13. ALTERNATIVES TO STUDY PARTICIPATION

The subject's alternative to participation is to not join the trial or to discontinue the study and continue to receive care for their HIV from their doctor. Subjects can also enroll in other clinical trials that may be ongoing that the subject may be eligible to enroll

14. POTENTIAL RISKS

Risk of Social Harm: Although we make every effort to protect the subject's privacy and confidentiality, it is possible that the subject's involvement in the study could become known to others. If this was to happen, the subject's family and/or communities may have problems accepting the subject's status. This could cause the subject to become labeled as HIV-infected or at high risk for HIV infection causing them to be treated unfairly or to be discriminated against, such as affect their employment and ability to obtain insurance.

Risks of Fasting: Some people find fasting to be difficult. It may make some people feel anxious, irritable, or hungry. Fasting may also cause dizziness, headache, stomach discomfort or fainting.

Risks of Test Results: Getting test results may make some participants feel worried or nervous. Because some tests are experimental, tests results cannot always be given to the subject. Laboratory results (e.g. tests that check the fats in your blood) will be given to the subject, when possible, after the study.

Unknown Risks: There may be unknown risks that are unforeseen, or at this time cannot be predicted. The subject will be told of any significant new risks.

Risks of Lumbar Puncture:

Risks include headache, vision problems such as blurred or double vision (rare), hearing problems (rare), pain, lowered blood pressure, allergic reaction to the anesthetic used to numb the skin for the spinal tap, fever, problems with urination or bowel movements, nerve injury (rare), infection (rare), bleeding (rare). This allergic reaction could include itching, hives, swelling, shortness of breath, difficulty breathing, changes in blood pressure and heart rhythm, loss of consciousness, or in a rare case, death.

Occasionally (about 5 in 100 times), participants may experience leaking of cerebrospinal fluid into the tissues of back after the procedure which is known as post-LP headaches. The headache is not dangerous, but can be uncomfortable. You will be given instructions on how to contact the on-call research clinician (7 days a week, 24 hours a day) if you experience this type of headache. Rarely (about 1 in 100 times) the headache pain may be severe and persistent enough to require an epidural blood patch. A blood patch is a procedure in which 1-3 teaspoons of blood is drawn from your arm and injected into your lower back. Your blood clots there to stop the fluid leakage that is causing the headache. The blood patch is performed by an anesthesiologist physician at the hospital.

Reporting Requirements:

If a subject is tested for Hepatitis B and C, there may be a chance they will be diagnosed with one of these infections. The study staff will talk with them about their options and provide them with referrals of doctors and/or facilities that can provide treatment for their hepatitis infection if they are found to have one of these infections.

Efforts will be made to keep their personal information confidential, however, all cases Hepatitis B or C must be reported to the public health department. According to California state law, study staff is required to report their name, contact information and treatment records if their tests show evidence of active Hepatitis B or C.

Risk of Blood Draws

Risks include pain, bruising, fainting, swelling, dizziness or possible infection at the blood withdrawal sites (rare).

Risks of Stribild

Common adverse drug reactions in clinical studies (incidence ≥5%; all grades) nausea (16%), diarrhea (12%), abnormal dreams (9%), headache (7%), fatigue (4%), rash (3%), insomnia (3%), and dizziness (3%). Laboratory abnormalities can also occur including elevations in creatine kinase (7%), elevated amylase (3%), and hematuria (3%). Serious adverse events, including lactic acidosis and severe hepatomegaly, have been reported but are uncommon.

15. RISK MANAGEMENT PROCEDURES AND ADEQUACY OF RESOURCES

We will implement the following procedures to safeguard the patients against risk. In order to maintain subject confidentiality all laboratory specimens, evaluation forms, reports, and other records will be identified by a coded number only. All records will be kept in a locked file cabinet. Any information obtained as part of this study will not be released without written permission of the subject, except as necessary for monitoring by the UCSD IRB or for monitoring by the FDA. Please see the data security plan in section 16 for more information.

Experienced phlebotomists will obtain blood specimens.

Risks and reported adverse events of Stribild will be clearly explained to each subject during the informed consent process. At each study visit the study nurses will ask participants to report any symptoms they experience while taking Stribild. During PK visits, a temporary intravenous catheter will be placed in the subject's arm to facilitate multiple blood draws and minimize pain and swelling associated with repeated venipuncture. The intravenous catheter will be removed at the end of the 6-hour blood collection. Participants will be instructed to contact the Clinical Trials Unit in the event of adverse events by telephone 24 hours a day/7 days a week. Following a telephone interview, the Clinical Trials Unit will schedule a visit for an additional assessment as necessary. For serious adverse events participants, will be instructed to immediately discontinue Stribild and to go the closest emergency room. Any Grade 3 or higher symptoms or laboratory abnormalities will result in termination of Stribild. Subjects who experience renal function abnormalities with

estimated creatinine clearance below 50 ml/min will also have the study drug terminated and complete the evaluations listed in Section 4.2. Subjects will also have the study drug terminated in cases of suspected drug-related toxicity, taking prohibited concomitant medications (see section 4.2 of the master protocol), if a female subject is pregnant or breast-feeding, if the subject is judged by the investigators to be at significant risk of failing to comply with the provisions of the protocol as to cause harm to self or seriously interfere with the validity of the study results, at the discretion of the investigator, institutional review board (IRB), Food and Drug Administration, pharmaceutical sponsor; or if the subject requests to withdraw from the study. In case of injury or serious adverse events, the investigators will assist the subject in obtaining appropriate medical treatment.

Lumbar Punctures: Experienced research clinicians (either a physician or a nurse) will perform all lumbar punctures. Local back pain will be minimized by injection of an anesthetic, 1% lidocaine into the subcutaneous tissue surrounding the needle puncture site. Oral analgesics and anti-inflammatory medications will be provided when necessary. Following LP, patients will be observed for 10-15 minutes. Over 3,000 LPs have been performed at the HNRC using non-cutting or "pencil point" spinal needles that reduce the risk of post-LP cephalgia. A site clinician will be available by pager 24 hours-per-day to respond to problems, should they occur. If post-LP headache occurs, initial conservative management will include recumbency, hydration, and oral analgesics. When headaches are prolonged, a blood patch, involving an epidural injection of a sample of the subject's own blood, may be performed by consulting anesthesiologists.

UCSD AVRC will serve as the lead/coordinating site for this study. Clinics at the Erie County Medical Center and University of Rochester will be subordinate sites, as outlined in the master protocol team roster. All adverse events, protocol deviations, and other study related reports will be reviewed by the PI as outlined in section 5.0 of the Master Protocol. All data transfers and other study related information will be performed in accordance with the Data Security Plan.

The safety and tolerability of the study medications will also be monitored closely by the protocol team. In addition, a Data Safety Monitoring Board (DSMB) will be convened at two timepoints (after 50% enrollment, after completion of enrollment) to review the project's safety data. At least three experts will comprise the DSMB: a statistician with experience in clinical trials, an expert in HIV clinical trials, and an expert in neurologic HIV disease research. Reports will be prepared by the DSMB and responses will be prepared by the protocol team.

Case report forms (CRF) will be provided for each subject. Subjects must not be identified by name on any study documents. Subjects will be identified by the Patient Identification Number (PID) and Study Identification Number (SID).

All data on the CRF must be legibly recorded in black ink or typed. A correction should be made by striking through the incorrect entry with a single line and entering the correct information adjacent to it. The correction must be initialed and dated by the investigator or a designated, qualified individual. Any requested information that is not obtained as specified in the protocol should have an explanation noted on the CRF as to why the required information was not obtained.

Monitoring

The investigators will review the research records for accuracy, completeness, and legibility. The investigators will also regularly inspect regulatory files to ensure that regulatory requirements are being followed.

The investigator will make study documents (e.g., consent forms, drug distribution forms, case report forms)

and pertinent hospital or clinic records readily available for inspection by the Food and Drug Administration (FDA), as required, for confirmation of the study data.

Serious Adverse Experience (SAE) Reporting

Serious Adverse Experiences will be documented on the Serious Adverse Experience (SAE) Reporting Form and submitted to the sponsor and the IRB within 24 hours of the investigator becoming aware of the event.

Safety Monitoring Plan

A safety monitor will be designated to review safety reports.

Data to be reviewed

On a quarterly basis, the monitor will be provided with reports of the following data:

- All hypersensitivity (e.g., rash) and renal events regardless of grade or causality;
- All ALT grades, concurrent ALT + bilirubin, eosinophilia, rash, and other data that could be associated with drug hypersensitivity reactions;
- Study drug discontinuations and reasons for discontinuation
- Serious adverse events (SAEs), grade 3-4 AEs
- Grade 3-4 laboratory abnormalities

Within 24 hours of the event, the IRB, the sponsor, and the independent safety monitor will be provided with reports on all SAEs or grade 4 lab abnormalities

Stopping Guidelines

StribildTM has previously been used in phase III clinical trials, has an excellent safety profile, and has received marketing approval from the US Food and Drug Administration. The safety in this small, investigator-initiated study is expected to reflect those in larger registration trials. In the event that an unexpected and serious safety signal emerges, such as more than 33% of subjects having SAEs requiring treatment discontinuation, the investigators will present the data to the DSMB and will strongly consider temporarily suspending or prematurely ending the trial.

Biohazard Containment

As the transmission of bloodborne pathogens can occur through contact with contaminated needles, blood, and blood products, appropriate blood and secretion precautions will be employed by all personnel in the drawing of blood and shipping and handling of all specimens for this study, as currently recommended by the Centers for Disease Control.

All infectious specimens will be sent using the ISS-1 SAF-T-PAK mandated by the International Air Transport Association Dangerous Goods Regulations-Packing Instruction 602. Please refer to individual carrier guidelines (e.g., FedEx, Airborne) for specific instructions.

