Telephone assessment				X	X	
HIV RNA, Plasma	X	X	X			X
CD4+ T-cell count	X		X			X
Drug resistance testing	X					
HIV RNA, CSF		X	X			X
HIV Dementia Scale		X				X
Study drug dispensing		X	X	X	X	X
Safety assessment			X			X
PK assessment			X			X

Signs and symptoms, laboratory results, and toxicities \geq Grade 2 will be recorded on the appropriate case report forms (CRFs).

Screening and Entry Evaluations

1) Screening Evaluations will occur within 28 days of study entry

- a) Details of the study will be carefully discussed with subjects during screening and the subject asked to read and sign an informed consent approved by the IRB at the participating institutions.
- b) Documented presence of HIV infection, as specified in Section 3.1.1 of the master protocol, prior to study entry.
- c) A brief medical history will be obtained and will include:
 - i) Previous diagnoses including liver disease, renal disease, fracture, osteoporosis, allergies, drug reactions, and most recent menses.
 - ii) Current prescription and non-prescription medications taken within 14 days prior to entry.
 - iii) Recent use of drugs of abuse or unprotected sexual contacts. Past use of needles.
 - iv) A signs-and-symptoms assessment, including: vital signs, height, and weight. Vital signs will include temperature, blood pressure, and pulse rate.

- d) 35 mL of blood and 15 mL of urine will be collected using standard methods.
- 2) The following laboratory tests must be performed within 28 days prior to study entry, unless otherwise noted:
- a) Hematology: hemoglobin, hematocrit, mean corpuscular volume (MCV), white blood cell count, differential white blood cell count, and platelet count.
- b) Blood chemistries: electrolytes, blood urea nitrogen (BUN), creatinine, glucose, phosphorus, and calcium.
- c) Liver function tests: total bilirubin, AST, ALT, alkaline phosphatase, and albumin.
- d) Coagulation: prothrombin time, international normalized ratio, partial thromboplastin time
- e) Urinalysis, including urine glucose and protein
- f) Estimated glomerular filtration rate (eGFR)
- g) For women of childbearing potential: Serum or urine pregnancy test.
- h) HIV RNA in blood plasma
- i) Lymphocyte subsets in blood (including CD4+ and CD8+ T-cell absolute counts and percentages)
- j) Hepatitis C and hepatitis B serologic testing
- k) Rapid plasmin reagent (RPR)
- 1) Drug resistance mutation genotyping in blood
- m) 5 mL of blood plasma will be stored at -80C.

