 - i) Hematology: hemoglobin, hematocrit, mean corpuscular volume (MCV), white blood cell count, differential white blood cell count, and platelet count.
 - ii) Blood chemistries: electrolytes, blood urea nitrogen (BUN), creatinine, glucose, phosphorus, and calcium.
 - iii) Liver function tests: total bilirubin, AST, ALT, alkaline phosphatase, and albumin.
 - iv) Urinalysis, including urine glucose and protein
 - v) Estimated glomerular filtration rate (eGFR)
 - vi) For women of childbearing potential: Serum or urine pregnancy test.
 - vii) HIV RNA in blood plasma
 - viii) HIV RNA in CSF
 - ix) CSF total leukocyte count and differential, CSF erythrocyte count, CSF total protein, CSF albumin, CSF glucose
 - x) Lymphocyte subsets in blood (including CD4+ and CD8+ T-cell absolute counts and percents)
- d) Pharmacokinetics: Detailed instructions for performing the pharmacokinetic studies are detailed in the *PK Sample Collection and Processing Document*. Briefly:

StribildTM containing elvitegravir (EVG) 150 mg will be administered in the morning after breakfast, *e.g.* 9:00 am, for study days 1-14. The precise times of dosing on days 11, 12 and 13 will be recorded.

On the morning of study day 14, subjects will hold their morning dose and will report to the clinical research center at approximately 8:00 a.m. An indwelling catheter will be placed in one arm of the subject for serial PK sampling. StribildTM will be administered later that morning immediately after a meal and the precise time of drug administration will be recorded.

Blood samples will be collected prior to StribildTM dosing, and at 2, 4, and 6 hours following StribildTM administration. The catheter will then be removed and a lumbar puncture will be performed within 1 hour of the last blood sampling (\sim 7 hours after StribildTM dosing). Subjects will then be discharged from the clinical

research center.

- e) Drug dispensing: Six additional weeks of study drug will be dispensed from the research pharmacy.
- f) Specimen storage: In addition to specimens collected for the required PK assays, 5 mL of blood serum, 10 mL of blood plasma, 5 mL of whole blood, 5 mL of urine, and 8 mL of CSF will be stored at -80C.

5) Events Between Week 2 and Week 24 Visits

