- a) The study coordinator will call study subjects at Weeks 8 and 16 (and more often at their discretion) to inquire about signs or symptoms of adverse effects as well as medication adherence. Results will be recorded on a CRF. If any symptoms are reported, the subject will be asked to come to the clinic to be evaluated by the study nurse and investigator (see Section 6.6 of the master protocol).
- b) Drug dispensing: Eight weeks of study drug will be dispensed at Weeks 8 and 16.
- c) HIV RNA in plasma: Study subjects will be asked to return to their primary care provider to obtain a measurement of HIV RNA in blood plasma per routine clinical care. This is anticipated to occur after approximately 12 weeks of treatment. Study subjects will be asked to bring a copy of the lab report to the research center. Alternatively and with the consent of the study subject, the research nurse will obtain the value from the clinic.

6) Week 24 Assessments

- a) A complete medical history and physical examination will be performed:
 - i) Prior diagnoses including liver disease, renal disease, fracture, osteoporosis, allergies, drug reactions, and most recent menses.
 - ii) Current symptoms including those of an active systemic illness (e.g., fever) and bleeding or easy bruising.
 - iii) Prescription and non-prescription medications taken within 14 days prior to entry.
 - iv) Vital signs, including temperature, blood pressure, and pulse rate, height, weight, and waist circumference.
- b) The HIV Dementia Scale will be performed.
- c) 75 mL of blood and 15 mL of urine will be collected by standard methods. 15 mL of cerebrospinal fluid (CSF) will be collected by lumbar puncture using aseptic technique and an atraumatic needle. Collection will follow a specific schedule as detailed in detailed in the *PK Sample Collection and Processing Document* and summarized in section 4.2.2 of the master protocol.
- d) The following laboratory tests will be performed:
 - i) Hematology: hemoglobin, hematocrit, mean corpuscular volume (MCV), white blood cell count, differential white blood cell count, and platelet count.
 - ii) Blood chemistries: electrolytes, blood urea nitrogen (BUN), creatinine, glucose, phosphorus, and calcium
 - iii) Liver function tests: total bilirubin, AST, ALT, alkaline phosphatase, and albumin.
 - iv) Coagulation: prothrombin time, international normalized ratio, partial thromboplastin time

- v) Urinalysis, including urine glucose and protein

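### The Grade 2 threshold for case report form recording is not reconciled with the all-grade rash, renal and ALT reports promised to the safety monitor, so Grade 1 events noted at visits may be missed

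*Combined protocol and SAP*

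**What the plan says.** Section 9 (Research Design and Methods) gives the general recording rule directly below the schedule of assessments. The sentence opens with "Signs and symptoms, laboratory results, and toxicities". An at-least sign follows, and the sentence ends "Grade 2 will be recorded on the appropriate case report forms (CRFs".

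Section 15 (Safety Monitoring Plan, Data to be reviewed) lists what the monitor receives each quarter. Two items carry no grade limit: "All hypersensitivity (e.g., rash) and renal events regardless of grade or causality" and "All ALT grades, concurrent ALT + bilirubin, eosinophilia, rash, and other data that could be associated with drug hypersensitivity reactions". Later items in the same list, for adverse events and laboratory abnormalities in general, are limited to grades 3 and 4.

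Three other places bear on what is captured:

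- Section 9, Events Between Week 2 and Week 24 Visits: the coordinator calls at weeks 8 and 16 "to inquire about signs or symptoms of adverse effects as well as medication adherence. Results will be recorded on a CRF". No grade threshold is attached.
- Section 15, opening paragraphs: "At each study visit the study nurses will ask participants to report any symptoms they experience while taking Stribild". The text does not say where the answers are recorded.
- Section 9, week 2 and week 24 assessments: each requires "Liver function tests: total bilirubin, AST, ALT, alkaline phosphatase, and albumin", together with creatinine, eGFR, urinalysis and a differential white cell count.

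**The concern.** The two rules set different floors for the same events. The grade 3-4 limits elsewhere in the Section 15 list show that the all-grade request for hypersensitivity, renal and ALT findings was deliberate. A Grade 2 floor on the CRF is enough for the grade 3-4 items. It is not enough for the categories that the plan chose to watch most closely.

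An omission would leave no trace. If a Grade 1 rash is not entered, the monitor's report looks the same as if no rash had occurred. Three sites apply the recording sentence, and they may read it differently, so a difference in low-grade rash between sites could reflect recording practice alone. In a study of 14 subjects, each such event is a noticeable share of the safety information.

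**Working it through.** The plan gives no figure to reproduce on this point. The check is to follow each promised category from observation to the monitor's report under the two readings of the Section 9 sentence.

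- **Narrow reading:** the threshold attaches only to the last item, toxicities. All signs, symptoms and laboratory results are recorded.
- **Broad reading:** the threshold attaches to all three items.

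| Promised to the monitor | How it is observed | Narrow reading | Broad reading |
|---|---|---|---|
| ALT at any grade, ALT with bilirubin, eosinophilia | Required laboratory tests, weeks 2 and 24 | On the CRF as laboratory results | Possibly not on the CRF below Grade 2, but the result exists and the grade can be derived from it |
| Renal events shown by laboratory tests | Creatinine, eGFR and urinalysis, weeks 2 and 24 | As above | As above |
| Rash or other symptoms reported by telephone | Calls at weeks 8 and 16 | On a CRF, no threshold | On a CRF, no threshold |
| Rash or other hypersensitivity noted at a visit | History, examination and nurse questioning | On the CRF as a sign or symptom, unless the site classes it as a toxicity | Grade 1 not on the CRF |
| Renal event without a laboratory finding, noted at a visit | As above | As above | Grade 1 not on the CRF |

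The first three rows can reach the monitor under either reading, provided that the report may draw on laboratory results; the Research Plan does not say whether it does. The last two rows are the real exposure. They are lost under the broad reading, and are at risk under the narrow reading if a site files a Grade 1 finding as a toxicity.

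**Scale.** Inputs: 14 subjects (Section 9) and rash in 3% (Section 14, Risks of Stribild, in a list headed as all grades). That heading also gives an incidence floor of 5%, which 3% does not meet, so the rate serves only as a guide. Assuming that it applies here and that subjects are independent:

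- Expected rash cases of any grade: 14 × 0.03 = 0.42.
- Chance of at least one: 1 − 0.97^14 = 1 − 0.653 = 0.347, about 35%.

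The documents give no split by grade, so the share that would be Grade 1, and therefore at risk of omission, cannot be computed. No corresponding calculation is possible for renal or ALT events.

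**The case against.** The strongest case on the other side is that there is no conflict. The at-least sign stands next to toxicities, and the narrow reading fits the rest of the plan better. HIV RNA, CD4 count and albumin are laboratory results that the secondary endpoints need, so a rule keeping all laboratory results below Grade 2 off the CRF would exclude endpoint data. Section 15 can also be read as a specific exception to a general rule, and nothing in it says that the monitor's report comes only from toxicity entries. Finally, the Research Plan defers adverse event review and symptom handling to Sections 5.0 and 6.6 of the master protocol, which is not among the documents reviewed and may contain the missing link.

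Much of this stands. It rules out two stronger inferences that a reader might draw:

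- *That the CRFs capture only Grade 2 or higher, so the listing cannot be produced.* The sentence does not force that reading, the telephone rule has no threshold, and laboratory grades can be derived from scheduled results.
- *That a Grade 2 listing would show the monitor only subjects who have already stopped.* This relies on the Grade 2 termination rule in Section 9 (Management of Selected Toxicities), which appears under the heading on bone effects, fat redistribution and immune reconstitution. Section 15 sets termination of the drug at Grade 3 or higher. Those passages contradict each other and must be reconciled, but that is a separate matter and cannot support this point.

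The objection does not remove the ambiguity. A better-fitting reading is not a recording instruction, and the narrow reading still leaves a Grade 1 finding classed as a toxicity below the floor. The Research Plan itself never says how a Grade 1 event seen at a visit reaches the monitor.

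**Conclusion.** The point holds as an unreconciled pair of rules with a narrow consequence. If the Grade 2 threshold is applied to all three items, the all-grade listing may be incomplete, chiefly for Grade 1 rash or other hypersensitivity and non-laboratory renal events noted at visits. Laboratory-based ALT, eosinophil and renal findings are recoverable from the week 2 and week 24 results, and telephone reports are already covered.

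The likely number of affected events is small and cannot be stated more closely than the any-grade rash figure above allows. No endpoint, sample size or 24-hour reporting of serious events and grade 4 laboratory abnormalities is affected. The conclusion assumes that the master protocol contains no instruction settling the matter; if it does, a cross-reference would be enough. The correction is worth making because it protects a safety report that the plan itself requires, at almost no cost.

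**What to change.** Amend the recording sentence in Section 9 to make three statements:

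1. All protocol-required laboratory values are recorded regardless of grade.
2. Hypersensitivity (including rash), renal and hepatic events are recorded on the CRF at any grade.
3. The Grade 2 threshold applies only to other toxicities.

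Then add to the Safety Monitoring Plan in Section 15 that the monitor's quarterly listing is drawn from these records.

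The new wording should not limit other laboratory results to Grade 2 or higher. Taken literally, that would leave HIV RNA, CD4 count and albumin off the CRF. It should also leave the telephone contact form without a threshold, as now.

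The cost is a revised CRF instruction at three sites and slightly more data entry for 14 subjects. Treatment, visits and sampling do not change.
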